1.2. Study Design

- Study BDCY is a Phase 3, open-label, 2-arm, parallel-design, randomized control study to investigate if LY3209590 is noninferior to insulin degludec in adult participants with T1D who are treated with basal-bolus insulin MDI therapy.
- This study consists of a 1-week screening period, a 2-week lead-in period, a 52-week treatment period, and a 5-week safety follow-up period.
- Participants will be randomly assigned in a 1:1 ratio to LY3209590:insulin degludec. All participants will be treated with basal-bolus MDI therapy, which will be titrated to glycemic targets and as clinically indicated for hyperglycemia.
- Participants will be stratified based on country, HbA1c stratum (<8% and \geq 8%) at screening Visit 1, CGM use prior to study entry (yes/no), and carbohydrate counting for prandial insulin dosing (yes/no).
- Rescue therapy will be considered during the treatment period if the participants meet the protocol criteria of severe, persistent hyperglycemia.
- If study intervention is permanently discontinued, the participant will be encouraged to continue participation in the study for continued monitoring. Both efficacy (including HbA1c) and safety data will continue to be collected per the schedule of activities in the protocol.

2. Statistical Hypotheses

The primary objective of this study is to test the hypothesis that LY3209590 is noninferior to insulin degludec on glycemic control as measured by change in HbA1c from baseline to Week 26 (Visit 22) in adults with T1D currently on basal-bolus insulin MDI therapy.

The null hypothesis ($H_{1,0}$) is the difference between LY3209590 and insulin degludec in the change in HbA1c from baseline to Week 26 (Visit 22) is greater than the noninferiority margin (NIM).

The NIMs of 0.4% and 0.3% will both be tested to meet different regulatory requirements. A 2-sided 95% confidence interval (CI) will be used for testing noninferiority.

Secondary hypotheses

The key secondary (multiplicity adjusted) objectives are to test the hypotheses that LY3209590 is superior to insulin degludec with respect to

- change in HbA1c from baseline to Week 26 (Visit 22)
 - $H_{2,0}$: the difference (LY3209590 - insulin degludec) ≥ 0.0
- time in glucose range between 70 and 180 mg/dL (3.9 and 10.0 mmol/L), inclusive, measured by CGM 4 weeks prior to Week 26 (Visit 22)
 - $H_{3,0}$: the difference (LY3209590 - insulin degludec) ≤ 0.0 , and
- the event rate of clinically significant nocturnal hypoglycemia (<54 mg/dL [3.0 mmol/L] or severe) during the treatment period up to Week 52 (Visit 29)
 - $H_{4,0}$: the relative event rate (LY3209590 versus insulin degludec) ≥ 1 .

These hypotheses and the primary hypothesis will be tested using a strategy to control the overall type 1 error.

2.1. Multiplicity Adjustment

A graphical approach (Bretz et al. 2009, 2011) for multiple comparisons will be used to ensure the strong control of the overall type 1 error rate for testing the primary and key secondary (multiplicity adjusted) objectives. The overall significance level (α) will be set to 0.05. The total α will be used for the primary objective first, then the α will be allocated and transitioned to other key secondary objectives once the primary objective is met. Therefore, the noninferiority test for the primary objective will be based on the 2-sided 95% CI. Once the upper limit of the 2-sided 95% CI is below the NIM, the noninferiority will be achieved, and the α of 0.05 will be distributed to test superiority for the key secondary objectives. If the p-value of the 2-sided test for one of the key secondary objectives is below the assigned α level, the superiority is demonstrated, and the assigned α level will be distributed to the remaining objectives. The iterative test procedure continues until none of the remaining objectives can be demonstrated with their preserved α or all objectives are demonstrated successful. The NIM of 0.4% (for the treatment regimen estimand) and 0.3% (for the efficacy estimand) will both be tested to meet different regulatory requirements. No multiplicity adjustments will be made for conducting separate analyses relative to the efficacy and treatment regimen estimands. Each estimand will have its own familywise error rate of 0.05.

For primary and key secondary efficacy objectives, the details of the type 1 error control strategy are illustrated in [Figure BDCY.2.1](#). No multiplicity adjustments will be made for evaluating other secondary and exploratory objectives, or for safety assessments.

[figure not shown]

Figure BDCY.2.1. Type 1 error control strategy for primary and key secondary efficacy endpoints.

3. Analysis Sets

The following analysis populations and datasets are defined for the purpose of analysis.

Analysis Populations/ Datasets	Description
Entered Population	All participants who sign the informed consent form.
Randomized Population	All randomized participants. Participants will be analyzed according to the treatment they were assigned.
Modified Intent-to-Treat (mITT) Population	All randomized participants who took at least 1 dose of LY3209590 or insulin degludec. Participants will be analyzed according to the treatment they were assigned.
Efficacy Analysis Set 1 (EAS1) for the treatment-regimen estimand	
The data will include
 
 the mITT population, excluding participants discontinuing the study treatment due to inadvertent enrollment, and all measurements, regardless of the use of study treatment or rescue medications
Efficacy Analysis Set 2 (EAS2) for the efficacy estimand on efficacy measures	
The data will include
 
 the mITT population, excluding participants discontinuing the study treatment due to inadvertent enrollment, and measurement up to the early discontinuation of study treatment or the initiation of rescue medication 
The data cutoff for participants who had intercurrent events is defined by the earliest date from the dates below for individual participants other than the analysis on study dose:
 
 the date of last study dose + 10 days for LY3209590, or +1 day for degludec the start date of the first rescue medication. 
The data cutoff for analysis on study dose is defined by the earliest date from below dates for individual participants:
 
 the date of last study dose the start date of the first rescue medication
Safety Analysis Set (SS)	
The data will include
 
 the mITT population, and all measurements, regardless of the use of study treatment or rescue medications

4. Statistical Analyses

4.1. General Considerations

Statistical analysis of this study will be the responsibility of Eli Lilly and Company (Lilly) or its designees. Any change to the data analysis methods described in the protocol will require an amendment ONLY if it changes a principal feature of the protocol. Any other changes to the data analysis methods described in the protocol, and the justification for making the change, will be described in this SAP or the clinical study report. Additional exploratory analyses of data will be conducted as deemed appropriate. Statistical analyses for Japan Addendum are described in Appendix 12 (Section 6.13).

Unless otherwise stated, the efficacy analyses will be based on either Efficacy Analysis Set 1 (EAS1, see the definition in Section 3) or Efficacy Analysis Set 2 (EAS2, see the definition in Section 3). For the treatment-regimen estimand, EAS1 will be used. Unless otherwise specified, for the efficacy estimand, other secondary, and tertiary efficacy measures, EAS2 will be used. The treatment comparison will be based on either the 2-sided test or 95% CI.

Unless otherwise noted, the safety analyses will be conducted on the Safety Analysis Set (SS; see the definition in Section 3). Percentages will be calculated using the modified intent-to-treat (mITT) population as the denominator. For events that are sex-specific, the denominator and computation of the percentage will include only participants from the given sex.

For continuous measures, summary statistics will include sample size, mean, standard deviation (SD), median, minimum, and maximum for both the actual and the change from baseline measurements. For certain variables that are considered to be log-normally distributed, the geometric mean and coefficient of variation (CV) will be provided instead. Either a mixed model for repeated measures (MMRM) model or an analysis of covariance (ANCOVA) model will be used to analyze continuous outcomes. Least-squares (LS) means and standard errors (SEs) derived from the analysis models will also be displayed. Treatment comparisons will be displayed showing the treatment difference LS means and the 95% CIs for the treatment differences, along with the p-values for the treatment comparisons. For certain safety laboratory measures, log-transformed values will be analyzed in the statistical model instead. The actual, change from baseline and percentage change from baseline will be presented using the derivation based on the output from the statistical model and the assumption of log-normality.

For categorical measures, summary statistics will include sample size, frequency, and percentages. Fisher's exact test or logistic regression will be used for treatment comparisons, unless otherwise stated. For laboratory values, both conventional (CN) and System International (SI) units will be presented. Therefore, both % and mmol/mol will be presented for HbA1c, and both mg/dL and mmol/L will be presented for glucose measurements.

In this study, negative binomial regression will be used to analyze the number of hypoglycemic episodes. Group mean, instead of LS mean, will be estimated, and the delta method will be used to estimate the SE of the group mean (Qu and Luo 2015). Group mean is defined as the mean response in the treatment group for the studied population. The difference between LS mean and group mean is that the LS mean estimates the response by taking the inverse link function on mean covariates, while the group mean takes the inverse link function on individual patient covariates first and then averages over all patients. For severe hypoglycemia, the empirical

method, based on exposure-adjusted rate (calculated by the total number of events divided by total exposure), may be used for treatment comparison if the number of episodes is too small and leads to convergency issues in the negative binomial regression model.

The table below describes the definition of baseline and postbaseline observations for different analyses.

Analysis	Baseline Observations	Postbaseline Observations
HbA1c (treatment-regimen estimand)	Baseline is the last non-missing assessment prior to or on the day of first dose of study treatment.	Planned measurements at Week 26 (primary endpoint, Visit 22) and Week 52 (secondary endpoint, Visit 29) in EAS1. Use unplanned measurements (on the same visit day) if there are no planned measurements. A multiple imputation approach will be used to impute missing observations at Week 26 (Visit 22) and Week 52 (Visit 29).
HbA1c (efficacy estimand)	Baseline is the last non-missing assessment prior to or on the day of first dose of study.	Weeks 2, 4, 12, 16, 26, 36, and 52 (Visits 5, 7, 15, 17, 22, 25, and 29) in EAS2 for MMRM. All planned measurements at scheduled visits will be included. Use unplanned measurements (on the same visit day) if there are no planned measurements.
CGM parameters (treatment-regimen estimand)	Baseline will be derived from the data collected prior to the first dose of study treatment. A multiple imputation will be used to impute missing observations at baseline.	The CGM values 4 weeks prior to Week 26 (Visit 22) and Week 52 (Visit 29) in EAS1. A multiple imputation approach will be used to impute missing observations at Week 26 (Visit 22) and Week 52 (Visit 29). See detailed derivations in Appendix 6 (Section 6.6).
CGM parameters (efficacy estimand)	Baseline will be derived from the data collected prior to the first dose of study treatment.	The CGM values prior to Weeks 4, 8, 12, 16, 22, 26, 32, 36, 40, 44, 48, and 52 (Visits 7, 11, 15, 17, 20, 22, 24, 25, 26, 27, 28, and 29) in EAS2 for MMRM. See detailed derivations in Appendix 6 (Section 6.6).
Basal insulin dose	The baseline period is the screening/lead-in period prior to the initiation of study treatment. The following variables will be derived: 
• daily dose in U• weekly dose in U, and• dose in U/kg/day. See a detailed derivation of variables in Section 4.4.2.1.	All scheduled visits between Week 0 (Visit 3) and Week 52 (Visit 29) in EAS2 for MMRM. The following variables will be derived: 
• daily dose in U• weekly dose in U, and• dose in U/kg/day See a detailed derivation of variables in Section 4.4.2.1.

Analysis	Baseline Observations	Postbaseline Observations
Prandial (bolus) insulin dose	
The baseline period is the screening/lead-in period prior to the initiation of study treatment.
 
The following variables will be derived:
 
 • daily dose in U • weekly dose in U, and • dose in U/kg/day. 
See a detailed derivation of variables in Section 4.4.2.1.
	
All scheduled visits after Week 0 (Visit 3) and up to Week 52 (Visit 29) in EAS2 for MMRM
 
The following variables will be derived:
 
 • daily dose in U • weekly dose in U, and • dose in U/kg/day 
See a detailed derivation of variables in Section 4.4.2.1.

Total insulin dose	
The baseline period is the screening/lead-in period prior to the initiation of study treatment.
 
The following variables will be derived:
 
 • daily dose in U • weekly dose in U, and • dose in U/kg/day. 
See a detailed derivation of variables in Section 4.4.2.1.
	
All scheduled visits after Week 0 (Visit 3) and up to Week 52 (Visit 29) in EAS2 for MMRM
 
The following variables will be derived:
 
 • daily dose in U • weekly dose in U, and • dose in U/kg/day. 
See a detailed derivation of variables in Section 4.4.2.1.

Basal/total insulin dose ratio	
The baseline period is the screening/lead-in period prior to the initiation of study treatment.
 
See a detailed derivation of variables in Section 4.4.2.1.
	
All scheduled visits after Week 0 (Visit 3) and up to Week 52 (Visit 29) in EAS2 for MMRM
 
See a detailed derivation of variables in Section 4.4.2.1.

Fasting glucose by SMBG	
The baseline period is the lead-in period up to the day of first dose of study treatment. Baseline will be derived as the average of all fasting glucose measurements between the Visit 2 date and the first dose date.
 
For treatment regimen estimand, multiple imputation will be used to impute missing observations at baseline.
	
For efficacy estimand, all available data from the day of first dose of study treatment up to Week 52 (Visit 29) in EAS2 for MMRM.
 
Values at each visit will be derived as the average of all fasting glucose measurements from the day post the prior visit up to the day of the visit.
 
For treatment regimen estimand data at Week 26 (Visit 22) and Week 52 (Visit 29) in EAS1 for ANCOVA with multiple imputation for missing data.

Laboratory values elevated or low, vital signs, and body weight categorical measures	
Starts from the screening visit and ends prior to or on the first dose date of the study treatment.
 
All available measurements at scheduled and unscheduled visits will be included. The baseline for weight will be the last non-missing value during the baseline period.
	
Starts after the day of first dose of study treatment and ends at the last visit in the study, including both the treatment period and follow-up period.
 
All available measurements at scheduled and unscheduled visits in the specified analysis period will be included.

Anti-LY3209590 antibodies	Refer to PSAP	Refer to PSAP
Patient-reported outcomes	Baseline will be the data collected at Visit 3.	
 • All scheduled visits after Week 0 (Visit 3) • Last collection after Week 0 (Visit 3)

Abbreviations: AE = adverse event; CGM = continuous glucose monitoring; CRF = case report form; EAS1 = Efficacy Analysis Set 1; EAS2 = Efficacy Analysis Set 2; HbA1c = hemoglobin A1c; MMRM = mixed model of repeated measures; PSAP = Program Safety Analysis Plan; SMBG = self-monitored blood glucose; TEAE = treatment-emergent adverse event.

All analyses will be implemented using SAS Enterprise Guide Version 7.1 or above.

4.2. Participant Dispositions

Reasons for discontinuation prior to randomization, including screen failure, will be summarized for all participants who sign the informed consent form but have not been randomized.

The number and percentage of participants who have completed/discontinued from the study/treatment will be summarized by treatment using the Randomized Population. The individual reasons for discontinuation will also be included in the summary. Comparison will be conducted using Fisher's exact test.

A listing of the reasons for study/treatment discontinuations will be generated for the Randomized Population. A listing of the randomized treatment for this study will also be provided.

Time to permanent discontinuation of study treatment, time to study discontinuation and time to early discontinuation of study treatment due to adverse events (AEs) (if there is a sufficient number to warrant a summary) will be presented as a figure.

4.3. Primary Endpoint Analysis

4.3.1. Definition of Endpoint(s)

The primary endpoint of this study is the HbA1c change from baseline to Week 26 (Visit 22). The HbA1c is reported in unit of percentage by central laboratory and will be converted to the unit of mmol/mol using the following formula:

$$HbA1c \text{ in mmol/mol} = 10.93 \times HbA1c \text{ in \%} - 23.5 \text{ (NGSP 2010).}$$

The HbA1c analysis will be conducted for both units.

4.3.2. Main Analytical Approach

The primary objective is to test the hypothesis that LY3209590 is noninferior to insulin degludec on glycemic control in the targeted study population. The noninferiority test will be based on either of the 2 estimands: ***treatment-regimen estimand*** for the US FDA submission and ***efficacy estimand*** for registrations in other countries. The full significance level of 0.05 will be used for each estimand.

This table provides the details of treatment-regimen estimand and efficacy estimand.

	Treatment-Regimen Estimand	Efficacy Estimand
Analysis Population	All participants in EAS1 with a non-missing baseline measure.	All participants in EAS2 with a non-missing baseline measure and at least 1 non-missing postbaseline scheduled measure.
Analysis Data	All non-missing observations at baseline and Week 26 (Visit 22) regardless of the use of study intervention or rescue medications.	All non-missing observations at baseline and all scheduled postbaseline timepoints during the treatment period (that is, Weeks 2, 4, 12, 16, 26, 36, and 52) (prior to the date of the last study dose + 10 days for LY3209590 (+1 day for degludec), or the initiation of rescue medication, whichever is earlier for participants with intercurrent events).
Missing Data	There may be missing values at Week 26 (Visit 22) due to early study discontinuation. The missing values will be imputed using multiple imputation by the retrieved dropout approach. The retrieved dropout participants are those who discontinue study intervention prior to Week 26 but have non-missing measures at Week 26. If there is only a limited number of retrieved participants (that is, at least 1 arm has <8 participants who discontinued study treatment early and have endpoint visit measurements) or the model cannot converge, the missing HbA1c at Week 26 will be imputed by return-to-baseline multiple imputation approach ^a .	There may be missing values due to the early discontinuation of the study intervention or use of rescue medication. The MMRM model will be used, and the missing values will be handled implicitly in the MMRM analysis under the assumption of missing at random.

	Treatment-Regimen Estimand	Efficacy Estimand
Analysis Model	After the imputation, the observed and imputed data will be analyzed by the ANCOVA model using treatment, strata (country, CGM use prior to study entry [yes/no], and carbohydrate counting for prandial insulin dosing [yes/no]), and baseline value of the dependent variable as independent variables. The statistical inference will be based on the multiple imputation framework by Rubin ^b .	The MMRM model will include treatment, strata (country, baseline, CGM use prior to study entry [yes/no], and carbohydrate counting for prandial insulin dosing [yes/no]), and visit and treatment-by-visit interaction as fixed effects and baseline of the dependent variable as a covariate. The Kenward-Roger approximation will be used to estimate denominator degrees of freedom for the MMRM models. An unstructured covariance structure will be used to model the within-participant errors. If this structure fails to converge, the following covariance structures will be used in order until one converges: 
 1. Toeplitz with heterogeneity 2. autoregressive with heterogeneity 3. compound symmetry with heterogeneous variances 4. Toeplitz 5. Autoregressive, and 6. compound symmetry without heterogeneous variances.

Abbreviations: ANCOVA = analysis of covariance; CGM = continuous glucose monitoring; EAS1 = Efficacy Analysis Set 1; HbA1c = hemoglobin A1c; EAS2 = Efficacy Analysis Set 2; MMRM = mixed model of repeated measures.

^a (Qu and Dai 2022)

^b (Rubin 1987)

The 2-sided 95% CI of the LS mean difference (LY3209590 - insulin degludec) in the HbA1c change from baseline to Week 26 (Visit 22) will be estimated. For both estimands, LY3209590 will be declared noninferior to insulin degludec if the upper limit of the 2-side 95% CI for the LS mean difference in the HbA1c (measured in %) change from baseline is below the NIM of +0.4%. In addition, the 95% CI for the LS mean difference will be compared to an alternative NIM of +0.3%.

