4.2. Scientific Rationale for Study Design

Primary endpoint

The primary efficacy measurement is HbA1c, a widely used measure of glycemic control that reflects a cumulative history of glucose levels in the preceding 2 to 3 months.

Overall design

Blinding

This is an open-label study. Investigators, participants, and study-site personnel will be unblinded to the assigned treatment. To eliminate potential biases, designated members of the Lilly study team will remain blinded throughout the study (see Section 6.3). Only a minimum number of Lilly personnel will see the randomization table and treatment assignments before the study is complete.

Study duration

The treatment duration is a reasonable timeframe to observe the effects of LY3209590 compared to insulin degludec.

The follow-up visits after the last dose is designed to capture any additional safety signals and to monitor the transition from study treatment to non-study insulins.

Comparator

Insulin degludec was chosen as the comparator because it is widely accepted as the best-in-class basal insulin. It has the longest half-life among other marketed basal insulins.

Collection of race and ethnicity data

In this study, collection of demographic information includes ethnicity (where permissible) and race. The scientific rationale is based on the need to assess variable response in safety and/or efficacy based on race or ethnicity. This question can be answered only if all the relevant data are collected.

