5.1. Inclusion Criteria

Participants are eligible to be included in the study only if all of the following criteria apply:

Age

1. Are at least 18 years of age at screening, or older per local regulations.

Type of participant and disease characteristics

2. Have a clinical diagnosis of T1D for at least 1 year prior to screening.
3. Have HbA1c value of 7.0% to 10.0%, inclusive, as determined by the central laboratory at screening.
4. Have received treatment with basal-bolus insulin analog MDI therapy according to the local product label for at least 90 days prior to screening
 - Allowed basal insulin analogs (includes biosimilars)
 - insulin glargine U-100
 - insulin glargine U-300
 - insulin degludec U-100 or U-200, or
 - insulin detemir
 - Allowed bolus insulin analogs (includes biosimilars)
 - insulin lispro U-100 or U-200
 - insulin aspart
 - insulin glulisine
 - fast acting insulin aspart (Fiasp® [Novo Nordisk A/S., Bagsvaerd, Denmark]), or
 - insulin lispro-aabc U-100 or U-200 (Lyumjev™ [Eli Lilly and Co., Indianapolis, IN]).
5. Are reliable and willing to make themselves available for the duration of the study and are willing and able to follow study procedures as required, including
 - adhere to the study basal-bolus insulin MDI regimen and use of study insulins according to injection instructions and protocol
 - use the CGM system supplied for this study for glucose monitoring, diabetes management, and data collection per protocol
 - maintain an electronic study diary and use the glucometer supplied for use in the study as required for the protocol, and
 - must have a normal wake/sleep pattern, such that midnight to 0600 hours will reliably reflect a usual sleeping period.

Weight

6. have a body mass index $\leq 35.0 \text{ kg/m}^2$ at the time of screening.

Contraceptive/barrier requirements

Contraceptive use by participants should be consistent with local regulations regarding the methods of contraception for those participating in clinical studies.

7. **Female participants:** for the contraception requirements of this protocol, see Section 10.4.

Male participants: no male contraception required except in compliance with specific local government requirements.

Informed consent

8. Capable of giving signed informed consent as described in Appendix 1, which includes compliance with the requirements and restrictions listed in the ICF and in this protocol.

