The MMRM model will include treatment, strata (country, CGM use prior to study entry [yes/no], and carbohydrate counting for prandial insulin dosing [yes/no]), visit and treatment-by-visit interaction as fixed effects, and baseline of the dependent variable (HbA1c) as a covariate.

The Kenward-Roger approximation will be used to estimate denominator degrees of freedom for the MMRM models. An unstructured covariance structure will be used to model the within-participant errors. If this structure fails to converge, the following covariance structures will be used in order until one converges:

1. Toeplitz with heterogeneity
2. autoregressive with heterogeneity
3. compound symmetry with heterogeneous variances
4. Toeplitz
5. autoregressive, and
6. compound symmetry without heterogeneous variances.

The 2-sided 95% CI of the LS mean for individual treatment groups and treatment LS mean difference for the HbA1c change from baseline to Week 26 (Visit 22) will be estimated. For both estimands, LY3209590 will be declared noninferior to insulin degludec if the upper limit of the 2-sided 95% CI for the LS mean difference in the HbA1c change from baseline is below NIM (+0.4% or +0.3% for different regulatory requirements).

The HbA1c is reported in % units and will be converted to mmol/mol using this formula.

$$\text{HbA1c in mmol/mol} = 10.93 \times \text{HbA1c in \%} - 23.5 \text{ (NGSP IFCC Standardization of HbA1c page [www.ngsp.org/ifccngsp.asp])}$$

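### The efficacy-estimand HbA1c MMRM fits one baseline slope to every visit from Week 2 to Week 52; a baseline-by-visit term would probably recover a little precision at Week 26 at almost no cost

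*SAP*

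**What the plan says.** SAP 4.3.2 analyses the efficacy estimand by MMRM on all scheduled post-baseline HbA1c values ("that is, Weeks 2, 4, 12, 16, 26, 36, and 52"). The mean model has treatment, strata, "visit and treatment-by-visit interaction as fixed effects and baseline of the dependent variable as a covariate". Protocol 9.3.2 gives the same model: "visit and treatment-by-visit interaction as fixed effects, and baseline of the dependent variable (HbA1c) as a covariate". Neither document crosses baseline with visit. The word baseline also stands alone in the SAP's list of strata; whatever it denotes, it is not crossed with visit either.

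On the covariance, the SAP states: "An unstructured covariance structure will be used to model the within-participant errors", with simpler structures as fallbacks.

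Protocol 4.2 describes HbA1c as a measure that "reflects a cumulative history of glucose levels in the preceding 2 to 3 months".

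The same MMRM serves the efficacy-estimand superiority test of HbA1c (SAP 4.4.1.2) and HbA1c at Week 52 (SAP 4.4.2.1). The treatment-regimen ANCOVA uses baseline and Week 26 only, so it fits its own Week 26 slope and is not affected.

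**The concern.** A single slope assumes that baseline HbA1c predicts Week 2 and Week 26 equally well. The protocol's own account of HbA1c makes that unlikely. At Weeks 2 and 4 the measurement still largely reflects glucose before randomization, so the slope of HbA1c on baseline should be near 1. By Week 26, after the 12-week titration period, it should be lower.

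The common slope is not a simple average over visits. Generalized least squares favours visits with small residual variance, and those are the early ones. Week 26, the primary time point, can therefore be adjusted with what is close to the Week 2 slope. Baseline variation that should have been removed then stays in the Week 26 residual.

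At stake is the width of the Week 26 interval in the primary analysis for registrations outside the US. SAP 2.1 pairs that estimand with the 0.3% margin, where the stated power is at least 90% rather than at least 99%.

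**Working it through.** **Inputs from the documents.** 284 completers per arm, SD 1.1%, margins 0.4% and 0.3%, true difference 0 (SAP Section 5). Alpha: "The full significance level of 0.05 will be used for each estimand" (SAP 4.3.2), with noninferiority read from the two-sided 95% interval (SAP Section 2). Seven visits and unstructured covariance (SAP 4.3.2).

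**Inputs not in the documents, so assumed.** Visit-specific baseline slopes, baseline SD, residual SDs and visit correlations. The entry criterion ("Have HbA1c value of 7.0% to 10.0%, inclusive") limits the baseline SD; 0.6 to 0.9 was used.

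**Step 1: the plan's own power.** SE = 1.1 × √(2/284) = 0.0923.
- Margin 0.4%: Φ(0.4/0.0923 − 1.96) = Φ(2.37) = 99.1%.
- Margin 0.3%: Φ(0.3/0.0923 − 1.96) = Φ(1.29) = 90.1%.

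Both stated figures reproduce.

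**Step 2: formulas.** Let β be the vector of true visit slopes, S the residual covariance when each visit has its own slope, and v the baseline variance. Maximum likelihood with a common slope and unstructured covariance converges to

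b = (1′S⁻¹β) / (1′S⁻¹1).

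The Week 26 variance is S26 + v(β26 − b)² with the common slope, and S26 with baseline-by-visit. The ratio is 1 + v(β26 − b)²/S26.

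Two visits show the mechanism. With early SD a, late SD c and correlation r, the late visit's weight is proportional to a(a − rc). It is zero when r = a/c and negative when r is larger. The common slope can therefore lie at, or even beyond, the early slope.

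**Step 3: central case.** Assume baseline SD 0.75, Week 26 SD of change 1.1, slope of change on baseline running from −0.08 at Week 2 to −0.40 at Week 26 (0.92 to 0.60 on the HbA1c scale), and correlation 0.85 per doubling of time. The common slope comes out at −0.034.
- S26 = 1.21 − 0.5625 × 0.16 = 1.120, SD 1.058.
- Common slope: 1.120 + 0.5625 × (0.366)² = 1.195, SD 1.093.
- Variance ratio 1.195/1.120 = 1.067; interval ratio √1.067 = 1.033.
- Power at margin 0.3%: 90.5% as planned, 92.2% with the interaction.

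With no baseline adjustment at all the SD is 1.100, so in this case the planned covariate does little at Week 26.

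**Step 4: range.** Assume baseline SD 0.7 (v = 0.49), Week 2 slope 0.95 on the HbA1c scale, Week 26 residual SD 0.7 to 1.0, and correlation 0.7 to 0.85 per doubling of time.

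| Week 26 slope | Common slope | Smallest excess (residual SD 1.0) | Largest excess (residual SD 0.7) |
|---|---|---|---|
| 0.75 | 0.94 to 0.97 | 0.49 × 0.19² / 1.00 = 1.8% | 0.49 × 0.22² / 0.49 = 4.8% |
| 0.65 | 0.94 to 0.99 | 0.49 × 0.29² / 1.00 = 4.1% | 0.49 × 0.34² / 0.49 = 11.6% |

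These lie within 1% to 12% excess variance, and √1.01 to √1.12 is an interval 0.5% to 6% wider. A Week 26 slope of 0.50 gives about 10% to 25%.

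The correlations matter. With slope 0.65, baseline SD 0.7 and residual SD 0.7, a compound-symmetric correlation of 0.3 to 0.7 and a Week 2 residual SD of 0.25 to 0.5 gave 3.9% to 17%.

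Over a wider grid with the SD of change held at 1.1, the excess ran from 1% to 31%. Power at margin 0.3% was 88.8% to 92.4% as planned and 90.7% to 95.3% with the interaction. With equal slopes the loss was zero.

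**Step 5: simulation with dropout.** 400 trials per scenario, 335 per arm, about 12% missing-at-random dropout by Week 26. The ratio of interval widths (planned to interaction model) was 1.032 in the central case, 1.062 with the central slopes and residual SD 0.75, 1.127 with steep slopes and residual SD 0.75, and 1.000 with equal slopes. Mean estimates were within 0.004 of zero and coverage was 94% to 97% for both models.

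**The case against.** The strongest reply is that nothing is broken. Protocol and SAP agree, the model is conventional, and randomization keeps the treatment contrast unbiased whatever slope is used. That stands, and the simulation supports it. A reader might infer that Week 26 is adjusted wrongly enough to mislead; the results show no bias and no loss of coverage.

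A reader might also infer that the 0.3% margin is underpowered. SAP Section 5 does not support this. Its power rests on an SD of 1.1% with no stated credit for baseline adjustment, so the plan does not count on the precision at issue. The lowest planned-model value found was 88.8%, in an extreme scenario. With a Week 26 residual SD of 0.75, power is 97% or more under either model. SAP 4.3.2 also declares noninferiority at 0.4% for both estimands and treats 0.3% as the alternative, whereas SAP 2.1 pairs 0.3% with the efficacy estimand.

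The size is rightly contested: it depends on slopes and correlations that neither document gives, so only a range can be stated.

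Two extensions are not supported. One is that the common slope weakens the missing-at-random handling of dropouts; the dropout simulation showed no bias. The other is that the CGM, SMBG and insulin-dose MMRMs share the problem. The argument rests on HbA1c's long memory, which those measures lack, and SAP 4.4.2.1 sets compound symmetry for SMBG fasting glucose and insulin dose, so the pull toward low-variance visits does not arise there.

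**Conclusion.** The point holds as an efficiency improvement to one model. Both documents impose a common baseline slope on HbA1c from Week 2 to Week 52, and Protocol 4.2 gives good reason to expect unequal slopes. The likely price is a Week 26 interval wider by between half a percent and six percent. That rests on Week 26 slopes of about 0.65 to 0.75, a baseline SD near 0.7, residual SDs of 0.7 to 1.0 and correlations that decay with time. Lower Week 26 slopes or higher correlations raise it, and equal slopes remove it. The planned analysis would still give a valid noninferiority conclusion. The change is worth making because it uses data already collected and cost nothing measurable when the slopes were equal.

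**What to change.** In SAP 4.3.2, add a baseline HbA1c-by-visit interaction to the efficacy-estimand HbA1c MMRM, with the Week 26 treatment difference still taken from treatment-by-visit. State that the same model applies to HbA1c superiority (4.4.1.2) and to HbA1c at Week 52 (4.4.2.1). Leave the CGM, SMBG and insulin-dose models as they are. In the same edit, clarify or delete the word baseline that stands alone in the strata list.

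The change should be made before unblinding. It departs from the model in Protocol 9.3.2, so SAP 4.9, which now reports no changes, should record it with a short justification, and the similar statement in SAP Section 1 should be brought into line. Protocol 9.3.1 allows changes that do not alter a principal feature to be documented in the SAP.

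The cost is six extra fixed-effect parameters (seven visit slopes in place of one) against about 570 completers, a few sentences of text, and no new data.
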